13.3 Analysis of Demographics and Other Baseline Characteristics

Demographic and baseline characteristics including gender, age, race, weight, height, and other parameters as appropriate will be summarized using descriptive statistics. No inferential statistics will be carried out. For continuous variables, descriptive statistics (number, mean, standard deviation, median, minimum, and maximum) will be provided. For categorical variables, patient counts and percentages will be provided. Categories for missing data will be presented if necessary.

13.4 Efficacy Analysis

Efficacy endpoints include ORR, DCR, DOR, PFS, and OS. No formal statistical tests will be performed for these efficacy endpoints.

ORR is defined as the proportion of patients who achieve CR or PR (determined by the investigator) during the study in response-evaluable population.

DCR is defined as the proportion of patients who achieve CR, PR, or SD (determined by the investigator) during the study in response-evaluable population.

DOR is the time from the date of first documentation of a PR or better to the date of first documentation of PD for responders (PR or better). Responders without documentation of PD will be censored at the date of last response assessment that is SD or better.

TTP is the time from the date of the first dose of study drug to the date of the first documentation of PD according to RECIST v1.1.

PFS is defined as the time from the date of the first dose of study drug to the date of first documentation of PD according to RECIST v1.1 or death due to any cause, whichever occurs first. Patients without documentation of PD or death will be censored at the date of the last response assessment that is SD or better.

OS is defined as the time from the date of first dose of study drug to the date of death due to any cause. Patients without documentation of death at the time of analysis will be censored at the date last known to be alive.

ORR and DCR will be summarized using descriptive statistics with 95% CIs. PFS and OS will be analyzed descriptively using the Kaplan-Meier method for the safety analysis set. DOR will also be analyzed using the Kaplan-Meier method for the response-evaluable analysis set.

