13.2 Analysis Sets

Safety analysis set: The safety analysis set will include all enrolled patients who receive at least 1 dose (even incomplete) of modakafusp alfa.

Response-evaluable analysis set: The response-evaluable analysis set is a subset of the safety analysis set including patients with measurable disease at baseline and at least 1 post-treatment response assessment.

PK analysis set: The PK analysis set will include those patients from the safety analysis set who have sufficient data to calculate at least 1 PK parameter for modakafusp alfa.

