7.2 General Principles

All statistical analyses will be conducted using SAS[®] Version 9.4 (SAS Institute, Cary, NC).

For categorical variables, the count and proportions of each possible category value will be tabulated. The denominator for the proportion will be based on the number of subjects in the analysis sets. For continuous variables, the mean, median, SD, minimum, and maximum values will be presented for all patients in the relevant analysis set.

Means and medians will be presented to 1 more decimal place than the recorded data. The standard deviations (SDs) will be presented to 2 more decimal places than the recorded data. Minimum and maximum are presented using the same number of decimal places as the recorded data. Confidence intervals about a parameter estimate will be presented using the same number of decimal places as the parameter estimate.

All confidence intervals, statistical tests, and resulting P-values will be reported as 2-sided. P-values should be presented to 3 decimal places, with values less than 0.001 presented as <0.001.

Baseline values are defined as the last observed value before the first dose of the study drug. The summary tables will include escalation cohorts, overall for dose escalation phase, safety lead-in cohort in expansion phase, and by expansion cohorts and overall for expansion phase and overall for both phases as appropriate.

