7.2.3 Methods for Handling Missing Data

For efficacy and safety data, no imputation of values for missing data will be performed. Imputation rules for incomplete dates are described in Appendix B.

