7.3 Analysis Sets

- Safety Analysis Set: The safety analysis set will include all enrolled patients who received at least one dose (even incomplete) of the study drug.
- Response evaluable Analysis set: The response evaluable analysis set is a subset of the safety analysis set including patients with measurable disease at baseline and at least 1 post-treatment evaluation.
- DLT Evaluable Analysis Set: patients who receive all Cycle 1 doses of modakafusp alfa or experience a DLT in Cycle 1 in the dose-escalation portion of the study; or patients who receive all Cycle 1 doses of modakafusp alfa in combination with pembrolizumab or experience a DLT in Cycle 1 in the safety lead-in portion of the study.
- Pharmacokinetic Analysis Set: patients from the safety analysis set who have sufficient data to calculate at least 1 PK parameter for modakafusp alfa.
- Immunogenicity-evaluable Analysis Set: Includes patients with a baseline and at least one post-baseline immunogenicity assessment.

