7.9 Efficacy Analysis

Response will be assessed according to mRECIST 1.1 for all patients. Response will also be assessed according to iRECIST for patients in Phase 2 expansion cohort.

Best Overall Response (BOR)

Best overall response is defined as the best response (per investigator assessment as defined by mRECIST 1.1 or iRECIST Criteria) recorded after the first dose of the study drug until a subsequent anti-cancer therapy. Response assessments after treatment discontinuation but before the initiation of a subsequent anti-cancer therapy should be included in the analysis of BOR. This will be ordered from best to worst: Complete Response (CR or iCR), Partial Response (PR or iPR), Stable Disease (SD or iSD), Progressive Disease (PD, iUPD or iCPD), Not Evaluable (NE or iNE).

Waterfall plots for best percentage change in the size of target lesions as per mRECIST 1.1 criteria will also be presented. The plot will have the following information:

1. Response,
2. Dose,
3. Cohort
4. Phase (escalation, safety lead-in or expansion).

Best overall response will be summarized and listed for all patients in the response evaluable analysis set. Overall response will be listed for all patients in the response evaluable set for each visit along with percentage change in the size of target lesions per mRECIST 1.1 criteria. If target lesion is believed to be present but too small to measure, a value of 5 mm is assigned per mRECIST 1.1.

Overall Response Rate (ORR)

The ORR is defined as the proportion of patients who have achieved the best response of CR or PR during the study per investigator assessment as defined by mRECIST 1.1 or iRECIST Criteria. The ORR will be summarized by frequencies and percentages for patients in the response evaluable analysis set. A binomial exact confidence interval will also be provided when possible.

Disease Control Rate (DCR)

The DCR is defined as the proportion of patients who have achieved the best response of CR, PR or SD during the study per investigator assessment as defined by mRECIST 1.1 or iRECIST Criteria. The DCR will be summarized by frequencies and percentages for patients in the response evaluable analysis set. A binomial exact confidence interval will also be provided when possible.

Duration of Response (DOR)

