The DOR will be tabulated for those patients with a CR or PR during the study per investigator assessment as defined by mRECIST 1.1 or iRECIST Criteria in the response evaluable analysis set with a reasonable number of responses. The DOR is defined as the number of days from the first documentation of a response until progressive disease or death, whichever occurs first. If a patient misses two consecutive disease assessments, then follow-up for the primary endpoint will be censored at the time of last non-progressive scan prior to the missed interval.

The censoring rules and censoring date in the analysis of DOR will be the same as for PFS and TTP.

$$\text{DOR (months)} = (\text{date of progression or death or censor} - \text{date of confirmed response} + 1) / 30.4375.$$

The Kaplan-Meier method will be used to estimate the distribution of DOR. The 25th, 50th (median), and 75th percentiles, and the corresponding 2-sided 95% confidence intervals (CIs) based on Brookmeyer and Crowley method (Brookmeyer and Crowley 1982), will be presented. The number of patients with events and the number of patients censored will be summarized. DOR for all patients with a response will be listed.

Progression Free Survival (PFS)

PFS is defined as the time from the date of first dose to the date of PD (or iCPD) (per investigator assessment as defined by mRECIST 1.1 or iRECIST Criteria) or the date of death due to any cause, whichever occurs first. Patients without documentation of PD (or iCPD) or death will be censored at the date of the last response assessment that is SD (iSD) or better, and prior to or on the date of initiation of alternative anti-cancer therapy if patients start new treatments. Patients with no post baseline response assessment will be censored on day 1.

$$\text{PFS (months)} = (\text{earliest date of progression or death or censor} - \text{date of first dose} + 1) / 30.4375.$$

The analysis of PFS will be based on the safety analysis set with a reasonable number of patients. The Kaplan-Meier method will be used to estimate the distribution of PFS. Kaplan-Meier survival curves, the 25th, 50th (median), and 75th percentiles, along with associated 2-sided 95% confidence intervals (CIs) based on Brookmeyer and Crowley method, and Kaplan-Meier PFS

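### The phase 2 primary ORR, and DCR, leave out treated patients with no post-treatment response assessment, so any bias is upward

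*Protocol*

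**What the plan says.** ORR by RECIST v1.1 is the primary efficacy endpoint of the phase 2 expansion (Protocol 5.2.1, SAP 5.1). Protocol 13.4 fixes its denominator: "ORR is defined as the proportion of patients who achieve CR or PR (determined by the investigator) during the study in response-evaluable population". DCR has the same denominator. SAP 7.9 agrees: "The ORR will be summarized by frequencies and percentages for patients in the response evaluable analysis set", with an exact binomial confidence interval, and DCR is handled likewise.

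Both documents define the response-evaluable set as a subset of the safety set. Protocol 13.2 limits it to "patients with measurable disease at baseline and at least 1 post-treatment response assessment". SAP 7.3 limits it to "patients with measurable disease at baseline and at least 1 post-treatment evaluation" and does not say what counts as an evaluation.

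Three other SAP statements bear on patients who were never assessed:

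- SAP 7.2 on proportions: "The denominator for the proportion will be based on the number of subjects in the analysis sets".
- SAP 7.2.3: "For efficacy and safety data, no imputation of values for missing data will be performed".
- SAP 7.9 on best overall response, whose scale includes a not-evaluable category: "Best overall response will be summarized and listed for all patients in the response evaluable analysis set".

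PFS and OS, in contrast, are analysed in the safety set. For PFS, and again for TTP, SAP 7.9 has a rule for these patients: "Patients with no post baseline response assessment will be censored on day 1".

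**The concern.** Measurable disease is an entry criterion (Protocol 7.1, criterion 5). In practice, then, the requirement for a post-treatment assessment is what removes treated patients from the response-evaluable set. Those removed are not a random sample. They are patients who died, began other therapy, withdrew, were lost, or stopped for clinical deterioration before an assessment. None can have a recorded response.

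The expansion cohorts have no control arm. The ORR will therefore be read against outside rates, such as the 15% to 20% for checkpoint-inhibitor rechallenge and the 30% to 40% for checkpoint inhibition in advanced melanoma cited in Protocol 4.4.3.2. A one-directional error in a single-arm primary estimate has nothing to offset it.

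The plan foresees these patients, because it gives them a censoring rule for PFS and TTP, but it gives them no place in ORR or DCR. The TTP rule has its own difficulty. SAP 7.9 analyses TTP in the response-evaluable set, which under the Protocol 13.2 wording cannot contain a patient without an assessment.

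**Working it through.** **Sizes.** Protocol 13.1.2 gives up to 25 patients in each of 3 cohorts plus up to 9 lead-in patients: 3 × 25 + 9 = 84, as stated. Adding the 30 phase 1b patients gives 114, also as stated. The plan gives no numerical ORR assumption in readable text, so there is no further figure to reproduce.

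**Does any rule bring unassessed patients back?** Four candidates were read against the set definition.

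1. SAP 7.2 ties the denominator to the analysis set, so it confirms the exclusion.
2. The not-evaluable category of best overall response is summarised only inside the response-evaluable set, so it cannot capture a patient who never entered that set.
3. SAP 7.9 counts assessments made after treatment stops and before new anticancer therapy. A patient who stops early, for toxicity for example, is not lost automatically. The rule does nothing for a patient with no assessment at all.
4. No readable section plans an ORR or DCR in the safety set.

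The no-imputation statement in SAP 7.2.3 points the same way, but the argument does not need it; the set definition alone removes these patients.

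**Direction.** Let N be the treated patients with measurable disease in a cohort, m those with no post-treatment assessment, and r the responders. All r responders are among the N − m assessed patients.

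- Plan: r/(N − m)
- All treated: r/N
- Ratio: N/(N − m), which is at least 1

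The plan's rate is strictly higher whenever m > 0 and r > 0. The same holds for DCR.

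**Size.** N = 25 is the planned cohort maximum. The values of m and r are assumed, because the documents give neither. Intervals are exact (Clopper-Pearson) 95%.

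| m | N − m | Ratio | ORR, 5 responders | DCR, 10 with disease control |
|---|---|---|---|---|
| 0 | 25 | 1.000 | 20.0% (6.8 to 40.7) | 40.0% (21.1 to 61.3) |
| 1 | 24 | 1.042 | 20.8% (7.1 to 42.2) | 41.7% (22.1 to 63.4) |
| 2 | 23 | 1.087 | 21.7% (7.5 to 43.7) | 43.5% (23.2 to 65.5) |
| 3 | 22 | 1.136 | 22.7% (7.8 to 45.4) | 45.5% (24.4 to 67.8) |
| 5 | 20 | 1.250 | 25.0% (8.7 to 49.1) | 50.0% (27.2 to 72.8) |

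Against the cited rechallenge range of 15% to 20%, 4 responders give 4/25 = 16.0% in all treated patients, 4/22 = 18.2% at m = 3 and 4/20 = 20.0% at m = 5. The denominator alone moves the estimate from near the bottom of that range to the top.

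**Is m > 0 plausible?** The first repeat scan is due at about week 6 (Protocol 9.3.14). Protocol 4.3.2.2 reports a median treatment duration of 3.14 weeks in 17 phase 1b patients. Those data are single-agent, all-comer and from an interim cut with some patients still on treatment. They show that stopping before the first scan can happen; they do not estimate m for phase 2.

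**The case against.** The strongest reply is that the response-evaluable denominator is a prespecified choice applied consistently in both documents, and that bias exists only relative to an all-treated target the plan does not claim. No formal test is made on ORR. The number in each analysis population is tabulated (SAP 7.4), and response assessments and population membership are listed by patient (SAP Appendix A). The all-treated rate is therefore one division away. This limits the consequence, but a primary endpoint should not have to be rebuilt by the reader.

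Second, m may be 0 or small. At m = 1 or 2 the ORR shift is 0.8 or 1.7 points, against an interval about 34 points wide (40.7 − 6.8 = 33.9). This stands, and no claim is made about the actual size.

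Third, the looser SAP wording might keep a patient who had an investigator's clinical evaluation but no scan, and might leave the TTP day 1 rule something to act on. Scans are also allowed when clinically indicated, and follow-up continues after stopping for reasons other than progression. These routes could make m smaller. They do not change the direction, and the two wordings still need to be aligned. The TTP inconsistency does rest on the Protocol 13.2 wording.

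Fourth, the futility rule may use the response-evaluable set, in which case a new primary denominator would differ from the one used for stopping. That text is redacted, so the link cannot be checked. Keeping the response-evaluable analysis alongside the new one covers this case.

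**Conclusion.** The concern holds. As written, ORR and DCR are calculated only in patients with a post-treatment assessment or evaluation. No readable text counts the other treated patients as non-responders or plans an all-treated rate. The upward direction follows from the definitions alone. The size depends entirely on m: at N = 25 the factor is 1.042 for one unassessed patient and 1.250 for five, and there is no effect if every treated patient is assessed. Because the analysis is descriptive, no error rate or power figure changes; what changes is the headline estimate and its interval. Nothing is concluded about the futility rule. This should be corrected, but it does not threaten the design.

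**What to change.** In Protocol 13.4 and SAP 7.9, define the primary ORR and DCR denominator as all treated patients with measurable disease at baseline in each cohort. Classify patients with no post-treatment response assessment as not evaluable for best overall response, count them as non-responders, and summarise best overall response in the same set. Keep the response-evaluable analysis as a sensitivity analysis, and report m per cohort.

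Use one wording for the response-evaluable set in Protocol 13.2 and SAP 7.3, and say whether clinical progression without a scan qualifies. State the TTP analysis set so that its day 1 censoring rule can apply. The sponsor should also confirm which denominator the futility rule uses, so that any difference from the primary analysis is explicit.

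The cost is wording in Protocol 13.2 and 13.4 and SAP 7.3 and 7.9, plus one extra table from data already collected. The reported ORR may be slightly lower, and a patient who leaves early for an unrelated reason will count as a non-responder.

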13.5 PK Analysis

13.5.1 PK Noncompartmental Analysis

Modakafusp alfa PK parameters will be estimated using noncompartmental methods with Phoenix WinNonlin. The PK parameters will be estimated from the concentration-time profiles for the PK analysis set. The following PK parameters will be determined, as permitted by data:

- C_{max} .
- t_{max} .
- AUC_{∞} .
- AUC_{last} .
- λ_z .
- $t_{1/2z}$.
- CL.
- V_{ss} .
- Accumulation ratio based on AUC_{τ} .

Modakafusp alfa PK parameters will be summarized using descriptive statistics. Individual modakafusp alfa concentration-time data and individual PK parameters will be presented in listings and tabulated using summary statistics by dose cohort. Individual and mean concentration-time profiles will be plotted by dose cohort.

13.5.2 PK Sampling Intended for Population PK Analysis

The PK data collected in this study are intended to contribute to future population PK analyses of modakafusp alfa. These population PK analyses may include data collected in other modakafusp alfa clinical studies. If applicable, the analysis plan for the population PK analysis will be separately defined, and the results of these analyses will be reported separately.

13.6 Pharmacodynamic Analysis

During the clinical development of modakafusp alfa, several biomarkers will be assessed to test for their correlation with safety and, if possible, with efficacy. Markers that will be studied are markers linked either to the drug itself or to the treated disease. Markers of immune system activation will be summarized using descriptive statistics. Individual data will be listed. Summaries will be provided separately for each study phase and by dose, as applicable.

13.7 PK/Pharmacodynamic Analysis

Exposure-response relationships between modakafusp plasma exposure and pharmacodynamic response (eg, RO, degree of immune activation, changes in cytokines/chemokines, gene expression changes) may be explored on an ongoing basis as PK and pharmacodynamic data become available to understand the PK-pharmacodynamic relationship of modakafusp alfa and to help in estimation of the PAD. Data permitting, mathematical models may be used to describe this relationship and such models may be used to predict the dose of modakafusp alfa that provides the desired exposure and pharmacological response for future evaluation. If applicable, these data may be presented graphically as well as summarized in the clinical study report.

13.8 PK/QTc Analysis

The PK-time matched triplicate ECG data collected in each patient during the dose escalation phase will be pooled to understand the PK-QTc interval relationship of modakafusp alfa. The relationship between modakafusp alfa plasma concentration and effects on heart rate and QTcF interval will be analyzed using nonlinear mixed effects modeling. These population PK-QTc interval analyses may include data collected in other modakafusp alfa clinical studies. As such, the analysis plan for the population PK-QTc interval analysis will be separately defined, and the results of these analyses will be reported separately and not presented in the clinical study report for this study.

13.9 Immunogenicity Analyses

The proportion of patients with positive ADA (transient and persistent, titer and specificity) during the study will be summarized. The effect of immunogenicity on modakafusp alfa and pembrolizumab PK, pharmacodynamics, safety, and efficacy will be examined, if possible.

Analysis will be based on available data from patients with a baseline assessment and/or postbaseline immunogenicity assessment (safety analysis set). Summaries will be provided separately for each study phase and by dose, as applicable. These analyses will be exploratory in nature, and all results will be descriptive in nature.

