Based on available ADA data in Study 1001, six of eight (75%) patients were ADA positive post-treatment; all 6 patients were reported as ADA negative at baseline. No apparent dose-related increase in the ADA incidence was observed. The first incidence of ADA was observed at C2D1 for all post-treatment ADA, and both transient and persistent ADA were observed.

Exploratory analysis is going in the clinical studies to assess the impact of ADA on modakafusp alfa disposition, efficacy, and safety as more data are accrued.

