5.2.2 Secondary Endpoints

- MTD or PAD (as defined in 6.1.1), if available (phase 1b).
- RP2D for SA and in combination with pembrolizumab, respectively (phase 1b and phase 2 safety lead-in).
- Frequency and severity of TEAEs according to the NCI CTCAE v5 (phase 2 expansion).

- Number/percentage of patients with 1 or more SAEs (phase 2 expansion).
- Number/percentage of patients with 1 or more TEAE leading to dose modification and/or treatment discontinuation (phase 2 expansion).
- PK parameters after the first dose of modakafusp alfa on Cycle 1 Day 1 (C1D1) and on Cycle 2 Day 1 (C2D1) for dose escalation phase (phase 1b) and on Cycle 1 Day 1 (C1D1) and Cycle 3 Day 1 (C3D1) for the phase 2 safety lead-in phase of dose expansion:
 - Maximum observed concentration (C_{max}).
 - Time of first occurrence of C_{max} (t_{max}).
 - Area under the plasma concentration versus time curve from time 0 to time t (AUC_t).
 - Area under the concentration-time curve from time 0 to infinity (AUC_{∞}).
 - Terminal disposition phase half-life ($t_{1/2z}$).
 - Clearance.
 - Volume of distribution at steady state (V_{ss}).
- ORR (CR + PR) assessed according to the RECIST v1.1 for patients in dose escalation (phase 1b).
- Disease control rate (DCR) (CR + PR + stable disease [SD]) (phase 1b and phase 2).
- DOR (phase 1b and phase 2).
- TTP (phase 1b and phase 2).
- Progression-free survival (PFS) assessed according to RECIST v1.1 (phase 1b and phase 2)
- OS (phase 1b and phase 2).
- Efficacy measures of ORR, DCR, DOR, TTP, and PFS based on iRECIST (phase 2 expansion).
- Anti-modakafusp alfa antibody incidence and titer (phase 1b and phase 2).

Definitions and timeframes of primary and secondary endpoints are provided in Section 6.3.3.

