7.11 Other Outcomes

7.11.1 Immunogenicity Analysis

The immunogenicity of modakafusp alfa will be assessed by determining anti-modakafusp alfa antibody incidence and characteristics (e.g., titer and specificity). All ADA data will be listed. For patients in the immunogenicity evaluable analysis set, percent of patients with positive ADA at each timepoint, as well as percent of patients with positive ADA by domain specific assay and ADA titers, will be summarized by dose levels by study phases (escalation and expansion). Percent of patients with positive ADA at baseline and at any post-baseline time point during the study will be reported. Additional summary tables and figures may be generated to assess the impact of anti-modakafusp alfa antibodies on the pharmacokinetic profile, drug efficacy, pharmacodynamic profile, and clinical safety will be evaluated, if possible. These analyses will be exploratory in nature and may be included in CSR if there is a trend.

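### ADA incidence, a secondary endpoint, has different denominators in protocol and SAP, and neither document's numerator separates new ADA from ADA already present at baseline

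*Protocol*

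**What the plan says.** ADA incidence and titer is a secondary endpoint for phase 1b and phase 2 in protocol 5.2.2 and in SAP 5.2.

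**Population.** Protocol 13.9 uses "available data from patients with a baseline assessment and/or" a postbaseline one, and labels this group the safety set. SAP 7.3 defines the immunogenicity-evaluable set differently: "Includes patients with a baseline and at least one post-baseline immunogenicity assessment". SAP 7.11.1 uses that set for its rates: "For patients in the immunogenicity evaluable analysis set, percent of patients with positive ADA at each timepoint". SAP 7.2 takes the denominator of a proportion from the number of subjects in the analysis set.

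**Numerator.** Protocol 13.9: "The proportion of patients with positive ADA (transient and persistent, titer and specificity) during the study will be summarized". SAP 7.11.1: "Percent of patients with positive ADA at baseline and at any post-baseline time point during the study will be reported".

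**Where the definition should be.** For this endpoint, protocol Table 6.a refers to Section 13.6. That is the pharmacodynamic section, and it does not define ADA incidence. Immunogenicity is in 13.9.

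**Interim result.** Protocol 4.3.3 reports that "six of eight (75%) patients were ADA positive post-treatment", and that all six were negative at baseline.

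**The concern.** There are two separate problems.

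The first is a conflict between the documents about who is counted. Under the protocol wording, a patient with only a baseline sample belongs to the analysis group but can never be found positive later. Under the SAP that patient is left out. A patient with only a later sample is in under the protocol and out under the SAP. The protocol label adds to the confusion, because its safety set (13.2) requires one dose and no ADA sample at all. The SAP summary of changes does not mention the different population.

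The second is a gap common to both documents. The post-baseline percentage counts anyone positive at a later time, including a patient who was already positive before treatment. The SAP requires a baseline sample for entry to its set, but uses the result only for a separate baseline percentage. For an endpoint called incidence, a reader wants the share of patients who became positive on treatment, and no planned summary gives it. The SAP sentence can also be read as asking for patients positive at both times.

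What is at stake is the meaning and comparability of a reported secondary endpoint. No hypothesis test rests on it.

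**Working it through.** **1. The plan's own figure.** 6/8 = 75.0%, which reproduces (Clopper-Pearson 95% CI 34.9% to 96.8%).

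**2. Can a patient have only a baseline sample?** Yes. The schedules of events collect ADA predose on Day 1 of each cycle, and at end of treatment only where possible. A patient who stops during Cycle 1 may have no later sample. The number of such patients is not given.

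**3. Effect of the denominator.** Let N be patients with a baseline sample, m those among them with no later sample, and x those positive later.

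- SAP rule: x/(N − m)
- Protocol rule: x/N
- Difference: SAP rate × m/N

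With N = 25 (the planned maximum per expansion cohort) and a SAP rate of 75%, one baseline-only patient costs 0.75 × 1/25 = 3.0 percentage points. With whole patients (x is 75% of N − m, rounded; m is assumed):

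| m | SAP rule | Protocol rule | Difference (points) |
|---|---|---|---|
| 0 | 19/25 = 76.0% | 19/25 = 76.0% | 0.0 |
| 1 | 18/24 = 75.0% | 18/25 = 72.0% | 3.0 |
| 2 | 17/23 = 73.9% | 17/25 = 68.0% | 5.9 |
| 3 | 16/22 = 72.7% | 16/25 = 64.0% | 8.7 |
| 5 | 15/20 = 75.0% | 15/25 = 60.0% | 15.0 |

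Patients with a later sample but no baseline sample can move the protocol rate either way. Starting from a SAP rate of 16/22 = 72.7%, three such patients give 16/25 = 64.0% if all are negative and 19/25 = 76.0% if all are positive.

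**4. Effect of the numerator.** Assume 25 patients with both samples, 18 positive at some later time, and b of those 18 already positive at baseline. The any-post-baseline figure is 18/25 = 72.0% whatever b is. Newly positive among baseline-negative patients is (18 − b)/(25 − b):

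- b = 1: 17/24 = 70.8%
- b = 2: 16/23 = 69.6%
- b = 3: 15/22 = 68.2%

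The two planned percentages do not fix this quantity. With 3 of 25 positive at baseline and 18 of 25 positive later, the newly positive rate is 15/22 = 68.2% if all three stay positive, and 18/22 = 81.8% if none of them is positive again.

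**5. Interim data.** All six positives were baseline-negative, so none would be reclassified.

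**The case against.** The strongest reply is that the matter is settled in practice. Protocol 13.0 leaves the detail of variables and methods to the SAP. The SAP names one set, applies it, and that set is the one recommended here. Protocol 13.9 also speaks of available data and does not state a denominator for post-baseline positivity. Much of this stands: the denominator half needs only an alignment of the protocol text. But changing the population goes beyond adding detail, and a reader of the protocol alone would expect a different rate.

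On the numerator, the SAP does report baseline positivity, positivity by time point and titers, and it lists all ADA data. Pre-existing antibody would therefore be visible, and the new-ADA count could be rebuilt from listings. Neither document calls the post-baseline percentage drug-induced. This too stands. The gap is in the planned summary, and because both documents share it, it is not a discrepancy between them.

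Two stronger readings are tempting and should not be made.

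- A reader might set the six positives over the 17 patients enrolled at the January 2021 cutoff and infer that the protocol rule could give 35%. That needs 17 − 8 = 9 baseline-only patients. Protocol 4.3.2.2 gives a median of 2 cycles among 17 patients, so the ninth-ranked patient had at least 2 cycles and at most eight had only one. Protocol 4.3.3 also describes the ADA data as what was available, so some results may simply have been outstanding.
- A reader might take the median treatment duration of 3.14 weeks as proof that many patients leave before a second sample. But 3.14 × 7 is about 22 days, roughly when Cycle 2 Day 1 falls in a 21-day cycle, and the same section reports the median of 2 cycles. Nor is there any figure to show that missing later samples differ by dose group.

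**Conclusion.** The point holds and is minor. The two documents define different populations for a secondary endpoint. The rates are certain to agree only when every patient has both samples. At about 75% positivity in a cohort of 25, the gap is about 3 percentage points per baseline-only patient, and 15 points with five of them. These counts are assumptions, because the documents do not give the actual number.

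Separately, the incidence of new ADA cannot be read from the planned summaries under either document. The size of that effect depends on how many patients are positive at baseline, which is also not given, and it touched none of the six interim positives. The ADA analysis is descriptive, so no error rate or sample size is affected.

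**What to change.** - **Protocol 13.9:** replace the sentence on the analysis population with the SAP 7.3 set (baseline plus at least one post-baseline sample), and drop the safety-set label.
- **SAP 7.11.1:** define ADA incidence as patients negative at baseline and positive at any later time, divided by the baseline-negative patients in that set. Show baseline-positive patients, with their titer change, on a separate line. Reword the present sentence so that it cannot be read as positive at both times.
- **Protocol Table 6.a:** change the reference for this endpoint from Section 13.6 to Section 13.9.

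The cost is wording in both documents and one extra table row. No additional samples or patients are needed.
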